	arrhythmias during FU)				• • •	Identification of optimal timing for any electrophysiological/arrhythmologic procedure Role of pharmacological antiarrhythmic treatment Role of aetiology-specific treatment on arrhythmic outcomes Identification of criteria for device implants (PM, ICD, S-ICD, CRT-D) in myocarditis patients Validation of therapeutic strategies and their optimal timing in patients with supraventricular arrhythmias, bradyarrhythmias, or ventricular arrhythmias Correlation between arrhytmia type/features with any other diagnostic exam performed at baseline or during FU (mainly EMB, CMR/DECT/PET, echocardiogram, stress tests,
					•	blood exams, genetic/blood/tissue/cell biomarkers) Indications and timing for device (ICD, CRT-D) implant in primary prevention, based on multiparametric risk assessment, and in relation to different general and aetiology- dependent treatments Other analyses
4	Evaluation of healing timing in myocarditis	500	•	Any degree of recovery by 3, 6, 9, 12 and > 12 months	• • • • •	Comparison of healing times in treated vs. untreated patients Correlations between healing times and clinical presentation types Correlations between healing times and any biomarker Correlations between healing times and any outcomes Validation of exercise stress test role after myocarditis healing Evaluation of PET scan or other diagnostic techniques as alternatives to CMR in special populations Other analyses
5	 Subrgoup analyses A. A vs. NA groups B. A myocarditis subgroups C. NA myocarditis subgroups (including fulminant) D. Infective vs. autoimmune vs. toxic forms E. Tretaed by aetiology- driven therapy vs. standard cardiological treatment 	500 (hugely variable in each subanalys is)	•	Differences in major outcomes	• • • • • •	Differences in minor outcomes Differences in any biomarker Differences in any diagnostic exam Differences in aetiology Differences in predisposition Differences in predisposition Differences in inflammatory activity Differences in pericardial involvement Differences in systemic involvement Differences in systemic involvement Differences in arrhythmias types and features Differences in clinical presentation Differences in treatment response, including novel treatments Validation of local aetiology/pathophysiology- dependent treatments (group E)

 F. Different myocarditis stages and differential diagnoses G. Isolated vs. in the context o a systemic disease or genetic disease H. Myocarditis vs. perimyocardis/ myopericarditis 	 Validation of biomarkers and imaging techniques in monitoring response to treatment (group E) Identification of optimal follow-up timeline Other analyses
-------------------------------------------------------------------------------------------------------------------------------------------------------------------------------------------------------------------------------------------------------	-------------------------------------------------------------------------------------------------------------------------------------------------------------------------------------------------

FOLLOW-UP VARIABLES

Any quantitative and qualitative parameters detectable by medical history, objetcive examination, biomarkers, 12-leads ECG, signal averaged ECG, continuous telemonitoring (during nwe hospitalization or in device carriers), Holter ECG (at least 24-hours, possibly 12-leads), color Doppler transthoracic echocardiogram, coronary angiography or CT scan, stress tests, CMR, DECT, PET scan (alone or in association/fusion), genetic tests, tilting test, electrophysiological study (either invasive or nonivasive), electroanatomical map, any other imaging or laboratory exam identified as clinically-relevant.

FOLLOW-UP TIMELINE

A clinical time zero (t0) will be considered as the start point for FU. t0 indicates the timing of myocarditis diagnosis, as assessed by EMB (first choice) or by imaging techniques (secondo choice).

FU calendar will be variable based on clinical indications. As a general line, intensive FU will be planned for the first two years (month 3, month 6, month 9, month 12, month 18, month 24). For patients needing a strict control for relevant clinical issues, minimal FU reassessment is set at 2 weeks timespan. In the absence of clinical issues, from month 24 FU will be performed every 6-12 months up to the end of the study.

FOLLOW-UP EXAMS

- Standard FU: cardiological (or multidiciplinary) assessment 1-2/y with blood exams (at least troponin, natriuretic peptides, and inflammatory indexes), 12-leads ECG, Holter ECG monitoring, device interrogation (in device carriers), and color Doppler transthoracic echocardiogram. Second-level imaging techniques (CMR, DECT, PET scan) or other exams will be performed based on clinical indications.
- Intensive FU: cardiological (or multidiciplinary) assessment 1-2/y with blood exams (at least troponin, natriuretic peptides, and inflammatory indexes), 12-leads ECG, Holter

ECG monitoring, device interrogation (in device carriers), and color Doppler transthoracic echocardiogram. Minimal reassessment timespan is 2 weeks. At least one second-level imaging techniques (CMR, DECT, PET scan) will be performed by 12 months (approximately at 3, 6, 9, or 12 months based on clinical indications). Exercise stress test will be performed whenever clinically indicated, usually not before proved myocarditis healing. Other exams will be performed based on clinical indications.

STUDY DURATION

Estimated study duration is 23 years (from Jaunary 2013 to December 2035). In detail:

- Retrospective enrollment: from January 2013 to local institute review board approval.
- Prospective enrollment: from local institute review board approval to Dicember 2025 (estimated enrollment end).
- FU duration per patient: 10 years.
- Estimated last FU for last enrolled patient: December 2035.

CONFOUNDING FACTORS

Not applicable.

EPIDEMIOLOGIC DATA

Because of multiple clinical presentations and heterogeneous diagnostic techniques, myocarditis incidence is widely variable [1].

At our institution, the mean rate of clinically suspected myocarditis is not inferior to 4 new cases/month. Epidemiology may be different at other centers.

Target numbers reported in Table 1 are reasonable.

DATA COLLECTION AND STATISTICAL ANALYSIS

Two enrollment modalities are accepted for this study: 1) prospective enrollment: at myocarditis diagnosis (following local institute review board approval); 2) retrospective enrollment: during FU of myocarditis patients (diagnosed before local institute review board approval).

Considering incidence rate, local and general epidemiology, enrollment of 1000 myocarditis cases by December 20205 is expected, including retrospective and prospective enrollment. For aim 1, 95% confidence intervals of 81-89% and of 75-85% are estimated for EMB and CMR, with 85% and 80% sensitivity, respectively. These data are consistent with updated knowledge. EMB will be considered as the diagnostic gold standard, as indicated [1].

Both baseline and FU data will be collected for each enrolled patient. CRF form reports the main study variables, in the form of an Excel document.

Statistical analyses will be performed by certified programs (i.e. SPSS).

Data will be presented as mean/median and standard deviation/interquartile range, or as contingency tables, depending on variables type and distribution. Parametric and non-parametric tests will be used accordingly. Confidence intervals will be set at 95%. Statistical significance threshold will be set at p < 0.05. Regression models will be used for univariable and multivariable risk stratification and survival analyses.

Either in all patients or in subgroups, appropriate statistical tests will be used for general and specific analyses, as needed to address each study aim (Table 1).

ETHICAL ISSUES

Our study will be performed in accordance with Helsinki Declaration and current laws regarding observational prospective and retrospective studies.

Diagnostic and therapeutical workup will not differ from daily clinical practice a tour hospital, as the result of updated international scientific evidence, integrated by the experience of a referral center for myocarditis and arrhythmias management, aiming at the best patients' interest. Follow-up timeline and diagnostic exams will be required as clinically needed. No randomization procedures will be performed. Patient grouping will be "spontaneous", based on clinical features and personalized overall workup. This study will respect the autonomy principle for any patient. At any time, patients will be free to accept or refuse any diagnostic or therapeutical proposal. As in daily clinical practice, critical or exceptional diagnostic and therapeutical options will be discussed in a multisiciplinary team and shared with patients, as needed. Per protocol, data will be simply collected and analyzed, without interfering with the best clinical practice. Thus, for any diagnostic exam or treatment, no special adverse reactions are expected, as compared to what observed in daily clinical practice.

Written informed consent will be obtained for any enrolled patient. No physical or psychosocial risks are expected regarding study procedures, informed consent, or authorization to use personal data.

Institutional review board evaluation is necessary to approve the present study protocol.

All data will be made anonymous. Analyses results will be published in international medical journals with impact factors.

REFERENCES

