- 3. Arrhythmic myocarditis is largely underdiagnosed and uninvestigated. Importantly, myocarditis presenting with arrhythmias requires specific diagnostic, prognostic and therapeutic considerations [2]. At our hospital, which is an international referral center for ventricular arrhythmias management and ablation, a relevant number of patients with unexplained arrhythmias had myocarditis as underlying aetiology. Our experience may considerably improve knowledge and management of arrhythmic myocarditis.
- 4. The role of CMR, as well as alternative nonivasive imaging techniques, in defining myocarditis healing is a relevant issue. In particular, optimal timing for follow-up diagnostic reassessment is still to be defined, in patients with myocarditis at different inflammatory stages, either with or without aetiology-dependent treatment [4,7].
- 5. Uniformly-designed studies are lacking, to compare myocarditis among different patient subgroups, differing by variables like: clinical presentations, myocarditis stage, associated cardiac or extra-cardiac diseases, aetiology-based treatment, associated arrhythmic manifestations, diagnostic workup, and devices or ablation treatment [8,9,10].

AIMS

Our study has multiple aims (full detail in Table 1).

- 1. To compare EMB with nonivasive diagnostic techniques (CMR, DECT, PET scan, either alone or in association).
- 2. To assess the role of blood biomarkers for identification of aetiology, predisposition, prognosis, response to treatment, inflammatory activity, clinical presentation.
- 3. To describe myocarditis presenting with arrhythmias, with special focus on ventricular arrhythmias at different myocarditis stages and in different clinical contexts. To validate and generalize our model for optimal diagnostic and therapeutical management of arrhythmias in myocarditis patients (given the role of our hospital as an international referral center for arrhythmias ablation and management).

- 4. To evaluate the timing needed for myocarditis healing in different patients subgroups, as assessed by nonivasive imaging techniques (CMR, DECT, PET scan), either alone or in association.
- 5. To compare patients subgroups of myocarditis, in terms of epidemiology, aetiology, prognosis, and diagnostic-therapeutical strategies. Among the others, the main study subgroups will be:
 - A. Arrhythmic vs. non-arrhythmic myocarditis.
 - B. Arrhythmic myocarditis subgroups.

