- Age \geq 18 years.

- Clinically suspected myocarditis [1].
- Enrollment performed by one of the participating Centers.

EXCLUSION CRITERIA

- Absence of written informed consent.
- Age < 18 years (paediatric population).

VARIABLES AND ENDPOINTS

The main study variables are reported in Table 1 and in CRF. Endpoints will include:

- Major endpoints: death; cardiac death; malignant ventricular arrhythmias (= VT, VF, appropriate ICD therapy); heart transplantation; end-stage heart failure.
- Minor endpoints: minor arrhythmias (NSVT; supraventricular arrhythmias; bradyarrhythmias); structural or functional myocardial abnormalities (any chamber dilation, systolic or diastolic dysfunction, including strain analysis, pericardial, vascular or valvular involvement, any other detectable abnormalities); abnormalities detectable by advanced imaging techniques (Lake Louise criteria and T-mapping techniques at CMR; any qualitative or quantitative imaging abnormality detectable by CMR, DECT or PET scan, or other imaging techniques, alone or in association); clinical variables (signs and symptoms related to cardiac or multisystemic disease; identification of associated diseases); blood exams abnormalities (inflammatory indexes; cardiac injury, inflammation or stress biomarkers; cardiac and extracardiac autoantibodies; genetic tests; tissue/organ damage indexes; markers of treatment toxicity; others); anatomical or functional abnormalities of coronary macro or microvascular structures (coronary angiography; CT scan; histology; provocative stress tests, nuclear medicine techniques); necessity of invasive elctrophysiological techniques (electrophysiological study; arrhythmia ablation; device implant) and related findings; indications and timing for primary and secondary prevention device implant, in relation with different therapeutic strategies; myocarditis recurrences; response to general and specific treatement; multiparametric modeling of prognostic risk stratification and response to treatment prediction; elaboration of multidisciplinary workup models.

The main pimary and secondary variables are reported in detail in Table 1.

Tabella 1

N	Aim	N patients	Primary Variables	Secondary variables

MYOCAR - Version V03 - Multicenter

Principal Investigators: [name] - [name]

1 Comparison between EMB 1000 Diagnostic Inflammation 	ory activity (presence; type;
and second level imaging concordance quantificat	
findings • Fibrosis (p	resence; type; quantification)

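### Aim 4 relates healing time to outcomes with follow-up counted from diagnosis, which builds in immortal-time bias whose direction depends on the contrast chosen

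*Protocol*

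**What the plan says.** The fourth item under Aims sets out "To evaluate the timing needed for myocarditis healing in different patients subgroups, as assessed by nonivasive imaging techniques", so healing is read from repeat imaging. In Table 1 the primary variable for aim 4 is "Any degree of recovery by 3, 6, 9, 12 and > 12 months". The secondary variables include "Correlations between healing times and any outcomes" and "Comparison of healing times in treated vs. untreated patients".

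Follow-up Timeline starts the clock at t0, the time of diagnosis by biopsy or, failing that, by imaging. For active myocarditis, Follow-up Exams asks for at least one second-level scan, which "will be performed by 12 months (approximately at 3, 6, 9, or 12 months based on clinical indications".

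Under Variables and Endpoints the major endpoints begin with death and cardiac death and end with "heart transplantation; end-stage heart failure". Patients of every severity are eligible, and Background expects a rapid adverse course in fulminant forms. Follow-up is 10 years per patient. Data Collection and Statistical Analysis names regression models for risk stratification and survival analyses, and lets retrospective patients enter while already in follow-up.

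**The concern.** Healing time is learned after t0, and only by patients who survive with their own heart to a scan that shows healing. From t0 to that scan, a patient later labelled as healed cannot by construction have died or been transplanted. If that protected time is credited to the label, a link with death or transplantation appears whether or not healing matters.

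The direction depends on the contrast. Healed versus not healed puts early deaths and transplants that precede a healing scan into the second group, so healing looks protective. Among the healed, those seen to heal at month 12 had to survive longer than those seen to heal at month 3, so slow healing looks protective. The two contrasts would mislead in opposite ways. Either could be published as a prognostic finding, or used to support the protocol's plans for follow-up timing and risk stratification.

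The problem is separate from irregular scan dates. It would remain if every survivor were scanned at every planned month.

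**Working it through.** The protocol has no figure to reproduce here: the target of 500 patients for aim 4 has no stated derivation, and no early death or transplant rate is given. The check asks what an analysis from t0 would show if healing had no effect at all.

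**From the protocol:** time origin t0; scans at 3, 6, 9 and 12 months; 10-year (120-month) follow-up; death and transplantation as outcomes.

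**Assumed:** latent healing time exponential with median 6 months; every survivor scanned at each planned month; risk of death or transplantation unrelated to healing, with a constant hazard λ1 in year 1 and λ2 later. For year-1 risk e and later annual risk a, λ1 = −ln(1−e)/12 and λ2 = −ln(1−a)/12 per month.

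**Step 1, healing months.** The share whose healing would first be visible at month s is q(s) = 0.5^((s−3)/6) − 0.5^(s/6). This gives 0.293, 0.207, 0.146 and 0.104 at months 3, 6, 9 and 12, a total of 0.75.

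**Step 2, events and time for a patient seen healed at month s.** Let S = exp(−λ1(12−s)).

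- Events: E(s) = 1 − S·exp(−108·λ2)
- Person-months from t0: P(s) = s + (1−S)/λ1 + S·(1−exp(−108·λ2))/λ2

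**Step 3, worked case: e = 15%, a = 2%** (λ1 = 0.013543, λ2 = 0.0016836).

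- Month-12 healers: 0.1663/110.75 = 0.001501. Month-3 healers: 0.2619/98.89 = 0.002649. Ratio 0.567.
- Healed versus not: weight each s by q(s)·exp(−λ1·s) and sum. Per enrolled patient, the healed have 0.1583 events over 71.03 months. All patients (s = 0) have 0.2913 over 95.01. The not healed therefore have 0.1330 over 23.98. Ratio = 0.002229/0.005546 = 0.402.

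**Step 4, all scenarios.** The last column is Σ q(s)·exp(−λ1·s); the figure among those event-free at 12 months is 75.0% throughout.

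| Year-1 risk | Later annual risk | Healed vs not, 10 years | Month-12 vs month-3 healers, 10 years | Healed by 12 months, all patients |
|---|---|---|---|---|
| 2% | 1% | 0.694 | 0.851 | 74.2% |
| 5% | 1% | 0.504 | 0.690 | 73.0% |
| 10% | 2% | 0.485 | 0.673 | 71.0% |
| 15% | 2% | 0.402 | 0.567 | 69.0% |
| 2% | 2% | 0.806 | 0.917 | 74.2% |
| 5% | 5% | 0.785 | 0.907 | 73.0% |

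The true ratio is 1 in every row. A simulation of 400,000 patients per scenario agrees: 0.41 to 0.79 for healed versus not over 10 years, and 0.23 to 0.41 over 24 months.

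**Step 5, the alternatives.** After month 12 the hazard is λ2 whatever the healing status, so a landmark there gives 1 in expectation; the simulation returned 0.98 to 1.02. Healing as a time-dependent status returned 0.97 to 0.99.

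**Step 6, the recovery proportion.** Counting all patients lowers it by 0.8 points (75.0 − 74.2) at 2% year-1 risk and by 6.0 points (75.0 − 69.0) at 15%. For comparison, the 95% half-width at N = 500 and a proportion of 0.75 is 1.96·√(0.75·0.25/500) = 3.8 points.

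**The case against.** The strongest reply is that this is absence of detail, not error. Denominators, competing events and landmarks are commonly left to a statistical analysis plan, which is not at hand, and the protocol promises tests suited to each aim. It nowhere says that unscanned patients are dropped or that healing is treated as known from t0. For the recovery proportion this largely stands: recovery by a given month reads naturally as cumulative, and can count earlier deaths as not recovered.

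It stands less well for the link to outcomes. There the protocol itself fixes the time origin, a variable learned only after it, and the fatal outcomes to which that variable is related. Read literally, those three together give the biased analysis.

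A second objection is also right: the text speaks of healing times, not of healed versus never healed, and among the healed the bias runs towards slow healing. That changes its direction but does not remove it.

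A reader might go further and infer that healing rates will be overstated, that healing will look protective through survival alone, or that a transplanted patient's normal donor heart will be counted as recovery. The documents do not support these. No survivors-only denominator is fixed, a real prognostic link may exist, and transplantation is itself an endpoint, with nothing to suggest that donor-heart findings count as healing. Nor is every early death a known non-healer, because any degree of recovery counts and reassessment can come as early as two weeks.

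**Conclusion.** The point holds for "Correlations between healing times and any outcomes" when time runs from t0 and the outcome is, or includes, death or transplantation. Under the assumed rates, with no true effect, the false 10-year rate ratio is 0.40 to 0.81 for healed versus not healed and 0.57 to 0.92 for month-12 versus month-3 healers. It is appreciable even at 2% year-1 risk. The actual size depends on early event rates, the healing-time distribution and scan timing, none of which the protocol gives. The contrasts are also the simplest readings of a loosely worded variable.

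For the primary variable the point is one of clarity: about 1 to 6 percentage points at 2% to 15% year-1 events, and within sampling error at N = 500 when early losses are about 5% or less.

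A related limit comes from the protocol's own enrolment rule. Retrospective patients enter during follow-up with written consent, so some early deaths may never be enrolled. No choice of denominator among enrolled patients recovers them.

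**What to change.** In Table 1, or in Data Collection and Statistical Analysis:

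- Relate healing to outcomes from a 12-month landmark among patients alive and transplant-free, or enter healing as a time-dependent covariate from the date of the scan that shows it. Apply the same rule to fast-versus-slow contrasts.
- Define the primary variable as the cumulative incidence of recovery at 3, 6, 9 and 12 months among all enrolled aim 4 patients with active myocarditis at t0, with death and heart transplantation before healing as competing events. Show the survivors-only figure beside it.
- Report prospectively enrolled patients separately, or account for delayed entry of retrospective patients.

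The cost is mainly analysis wording, and no clinical care changes. It does need dates of scans, death, transplantation and enrolment; the case report form is not shown, so confirm that these are captured. The landmark gives up first-year events and counts later healers as not healed at 12 months; the time-dependent model avoids that loss. The reported healing rate may fall slightly. Neither method removes confounding between healing and outcome.

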 - C. Non-arrhythmic myocarditis subrgoups (i.e.: fulminant, acute coronary syndrome-like, pericarditis-like, heart failure, nonischaemic dilated /hypokynetic cardiomyopathies of unknown aetiology...).
 - D. Infectious vs. aoutoimmune vs. toxic myocarditis.
 - E. Myocarditis treated by aetiology-based treatment vs. isolated cardiac medical treatment.
 - F. Myocarditis at different disease stages: acute, hyperacute, fulminant, chronic active, post-inflammatory, or active vs. previous vs. non-myocarditis.
 - G. Myocarditis presenting as organ-specific diseases vs. in the context of a genetic disorder or systemic disease.
 - H. Myocardits vs. peri-myocarditis/myo-pericarditis.
 - I. Other analyses.

STUDY DESIGN

Our study, previously designed as a single-center experience, is multicenter, observational and both retrospective and prospective.

Retrospective phase includes all clinical data occurring before the index event (hospitalization or clinically suspected myocarditis) and myocarditis diagnosis. Prospective phase includes all data following index event and myocarditis diagnosis.

Any adult patient with clinically suspected myocarditis, of any clinical presentation and any degree of severity, will be considered as suitable for study enrollment.

Patients will undergo diagnostic and therapeutical strategies considered as clinically indicated in a patient-tailored manner, as suggested by international guidelines recommendations and best local clinical practice. Patients will be free of either accepting or refusing any diagnostic or therapeutical proposal. Whenever accepted, data will be simply collected and analyzed.

Based on clinical presentation, patients will be divided into two groups, arrhthmic (group A) and non-arrhythmic (group NA, including any other clinical presentation).

Independently of A/NA groups, all patients will undergo optimal diagnostic and therapeutic strategies, as summarized in panel A. In parallel, special diagnostic and therapeutical strategies will be performed in patients with arrhythmic presentation or evidence of arrhythmias, as shown in panel B. Proposed flowcharts (panels A and B) represent only an approximate algorithm. Exceptions can be made in single cases, based on clinical indications.

Panel A – Diagnostic and therapeutical workup in all patients.

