Independently of groups (A/NA), all patients will undergo optimal diagnostic and therapeutical workup, guided by updated scientific evidence merged with the clinical experience of the center.

Baseline diagnostic workup will include: complete blood exams, 12-leads ECG, continuous telemetric monitoring, transthoracic doppler echocardiogram, coronary artery imaging (coronary angiography or CT scan). Any other clinically relevant diagnostic test will be collected.

In life-threatening presentations (cardiogenic shock or malignant arrhythmias), support treatment by optimal medical therapy, inotropic or mechanical circulatory support, and acute-phase arrhythmia management (including cardioversion, defibrillation, or temporary pacing) will be performed, as indicated, before completing diagnostic workup. Final diagnosis of myocarditis will include, whenever applicable:

- A. For stable patients: 1) a second-level imaging technique (CMR as first choice; and/or DECT, PET, or multiple/fusion imaging techniques, based on clinical indications); followed by: 2) EMB, whenever clinically indicated. Blood exams for aetiology screening will be personalized upon clinical indications.
- B. For unstable patients: EMB only, as recommended. Blood exams for aetiology screening will be personalized upon clinical indications.

Diagnostic criteria for myocarditis, as assessed by any diagnostic technique, will be defined based on international scientific evidence and will be constantly updated. Similar considerations apply to myocarditis staging and aetiology definition. Whenever not available at local institutions, diagnostic exams can be performed and analyzed at external centers.

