All patients with myocarditis (or any alternative final diagnosis), will undergo standard cardiological optimal medical treatment (COMT), as indicated. By converse, aetiology-dependent treatment will be performed only in patients with a final diagnosis of any *active* (acute, fulminant, chronic active) myocarditis of defined aetiology (EMB-proved). Multidisciplinary assessment, including infective disease specialists (in viral/infective myocarditis), immunologists (in non-infective/autoimmune myocarditis) or any other specialist as needed, will be used to identify indications to treatment, drug choice (either approved or with a justified off-lable indication), treatment duration and safety profile, aiming at the best patients' interest. Toxic myocarditis will be treated accordingly, by evaluating the opportunity of withdrawing pathogenic noxa.

This protocol will not interfere with local best clinical practice.

Patients with *non-active* myocarditis (previous or healed) or with non-myocarditis, will undergo "standard FU" (see below). Patients with *active* myocarditis will undergo "intensive FU" (see below).

Independently of FU modalities, diagnostic reassessment will be considered in the presence of at least one of the following *instability* criteria: a) new unexplained cardiac symptoms (dypnoea, chest pain, syncope, palpitation); b) new unexplained increase in troponin or natriuretic peptides; c) new imaging abnormal signs; d) new unexplained clinically relevant arrhythmias. Diagnostic reassessment will include second-level imaging and/or EMB, as shown above. Subsequent therapeutical workup will be in line with the above explanations. In stable patients or undergone myocarditis healing, exercise stress test will be obtained, whenever possible.

Panel B - Diagnostic and therapeutical workup of patients with arrhythmias

In parallel with (and independently of) Panel A content, patients with arrhythmias (group A) will undergo specific diagnostic and therapeutical management for arrhythmias, as a result of the integration between international guidelines recommendations and the experience of a third-level center international referral center (San Raffaele Hospital, Milan) for arrhythmia management and ablation.

To oversimplify, 4 groups of patients will be considered.

1. Group 1: major ventricular arrhythmias (haemodynamically unstable VT, hu-VT; ventricular fibrillation, VF).

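### Follow-up starts at the biopsy when there is one and at imaging otherwise, so in stable patients the clock depends on the step that opens access to aetiology-based treatment

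*Protocol*

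**What the plan says.** All references are to the protocol.

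- **Follow-up timeline:** "A clinical time zero (t0) will be considered as the start point for FU", and "t0 indicates the timing of myocarditis diagnosis, as assessed by EMB (first choice) or by imaging techniques (secondo choice").
- **Study design, Panel A, stable patients:** a second-level imaging test comes first, "followed by: 2) EMB, whenever clinically indicated".
- **Study design, Panel A, unstable patients:** "For unstable patients: EMB only, as recommended".
- **Study design, Panel A, treatment:** aetiology-dependent treatment is restricted to active "myocarditis of defined aetiology (EMB-proved").
- **Study design, Panel A, instability criteria:** "Diagnostic reassessment will include second-level imaging and/or EMB, as shown above".
- **Table 1, aim 4:** recovery is read by 3, 6, 9, 12 and more than 12 months, and a secondary variable is "Comparison of healing times in treated vs. untreated patients".
- **Aims, item 5E, and Table 1, aim 5:** patients given aetiology-based treatment are compared with those given cardiac treatment alone, with major outcomes as the primary variable.

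The statistical section names regression models for survival analysis in general terms. Confounding factors are declared not applicable.

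**The concern.** A comparison of two groups over time needs a time origin that does not depend on group membership. Here it does. A stable patient diagnosed by imaging alone is counted from the imaging date. A similar stable patient who goes on to a diagnostic EMB is counted from the later EMB date, and only that second patient can receive aetiology-dependent treatment.

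Two things follow in stable patients:

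- For a given healing date, the healing time recorded for a treated patient is shorter by the imaging-to-EMB gap.
- A major event in the gap cannot count against treatment. It either stops the patient from reaching EMB, leaving an untreated patient with an event, or it falls before the t0 of a patient treated later.

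At stake are the treated-versus-untreated part of aim 4, comparison 5E, and the related wish in Table 1 to validate local aetiology-dependent treatments.

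**Working it through.** The protocol states no figure on this point, so there is none to reproduce. The check has two parts: who is on which clock, and how large the distortion could be when treatment does nothing.

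**Clock by type of patient**

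| Patient | t0 | Offset from imaging | Can be treated |
|---|---|---|---|
| Stable, imaging only | imaging | none | no |
| Stable, imaging then diagnostic EMB | EMB | the gap | yes |
| Stable, imaging positive, EMB negative | imaging, since imaging made the diagnosis | none | no |
| Unstable, EMB only | EMB | none, no earlier imaging | yes |

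The offset arises in the second row. Some patients in that row stay untreated, because EMB is necessary but not sufficient for treatment.

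**A. Recovery read at time T after t0.** Recovery from the imaging date is taken as exponential with median m months, so F(T) = 1 − 2^(−T/m). A patient whose t0 falls L months after imaging shows F(T + L). The values of m and L are assumptions. For m = 6, T = 3 and L = 1: 1 − 2^(−3/6) = 29.3% against 1 − 2^(−4/6) = 37.0%.

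| Gap L (months) | 3 months, m = 6 | 12 months, m = 6 | 3 months, m = 9 |
|---|---|---|---|
| 0 | 29.3% | 75.0% | 20.6% |
| 0.25 | 31.3% | 75.7% | 22.1% |
| 0.5 | 33.3% | 76.4% | 23.6% |
| 1 | 37.0% | 77.7% | 26.5% |
| 3 | 50.0% | 82.3% | 37.0% |

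This is a pure shift of the clock: it keeps in the treated group anyone who would have recovered before EMB. Treatment requires active disease, so some of those patients might stay untreated, and that selection would pull the other way. If all of them were left out, the memoryless exponential would return the treated figure to F(T).

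**B. Major events.** Assumptions: 12-month risk from imaging 15%; half of patients planned for EMB at gap L and then treated; a patient with an event before EMB counted as untreated from imaging; censoring at 24 months; 1,000,000 simulated patients per scenario; Weibull shape 1.0 (constant hazard) or 0.5 (early events).

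| Gap L (months) | False rate ratio, constant hazard | False rate ratio, early events |
|---|---|---|
| 0 | 0.998 | 1.002 |
| 0.25 | 0.985 | 0.805 |
| 0.5 | 0.972 | 0.735 |
| 1 | 0.952 | 0.654 |
| 3 | 0.873 | 0.504 |

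Hand check at L = 1 with constant hazard: the monthly rate is −ln(0.85)/12 = 0.01354, so 1 − exp(−0.01354) = 1.345% of planned patients have an event before EMB. The untreated 12-month risk is (0.5 × 0.15 + 0.5 × 0.01345)/(0.5 + 0.5 × 0.01345) = 0.08173/0.50673 = 16.1%, against 15.0% in the treated. The simulation gave 16.1% and 15.1%.

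The L = 0 row removes both the clock offset and the wait for EMB. A common origin alone would not do this: a patient would still have to stay event-free until EMB to be labelled treated.

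**The case against.** **The gap may be short.** The protocol gives no gap, and the ratios from 0.985 to 0.504 rest wholly on assumed gaps and hazard shapes. A few days matter little with constant hazard. This stands, and it limits the size of the problem.

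**Not every treated patient is on a later clock.** Unstable EMB-only patients have no offset, biopsied untreated patients share the EMB clock, and the flowcharts are described as approximate. This stands. The offset is a feature of stable patients and the contrast is diluted.

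**A reset at reassessment is not stated.** A reader might infer that a patient diagnosed by imaging and biopsied months later for instability gets a new t0 after the triggering event. The text does not say so. That EMB is called a reassessment, follow-up is already running, and recurrences and minor arrhythmias are listed as endpoints, which a reset would undermine. The wording does not exclude a reset, so centres could code it differently, but no large bias should be charged to the protocol on this ground.

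**t0 may serve only the visit calendar, and the analysis plan may correct it.** The protocol does not say that every analysis is timed from t0. But it calls t0 the start of follow-up, and the recovery months of aim 4 are calendar months under that heading. A separate plan could add a correction. The protocol itself fixes t0 and states none.

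**Patients with a final diagnosis other than myocarditis have no t0.** This is a separate definitional gap and is not evidence of the bias described here.

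**Confounding by indication is probably larger.** Grouping is not randomised, so this remains on any clock. It does not justify adding an avoidable distortion.

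**Conclusion.** The point holds in limited form. Among stable patients the protocol's time origin depends on EMB, EMB is a condition for aetiology-dependent treatment, and nothing stated in the protocol brings the two clocks together. With no true effect, this tends to favour treatment in the healing-time comparison of aim 4 and in 5E. The direction is firmer for major outcomes. For healing it is that of a pure clock shift, and selection of patients with active disease could offset it.

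The size cannot be read from the documents. Under the stated assumptions it is negligible for a few days with constant hazard (ratio 0.985 at about a week). It becomes material for a gap of about a month (3-month recovery 37.0% against 29.3%) or when events come early (ratio 0.805 at about a week, 0.654 at one month). A reader might conclude that every treated patient is on a later clock, or that the comparisons are certainly and seriously biased. The protocol supports neither. The definition should be corrected, and the correction is cheap.

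**What to change.** 1. Define t0 by one rule that does not depend on the diagnostic method. One option is the date of the first positive diagnostic test, imaging or EMB, whichever is earlier. Another is the index event that the Study design section already uses to divide the phases ("all clinical data occurring before the index event (hospitalization or clinically suspected myocarditis")), fixed as a single date: the earlier of hospitalization and first clinical suspicion.
2. State that a later EMB, including one at reassessment, does not reset t0.
3. Record the imaging, EMB and treatment-start dates as separate variables. Whether the CRF already holds them cannot be checked, as it is not shown.
4. In treated-versus-untreated analyses, enter treatment as a time-dependent covariate or use a landmark. Moving t0 without this step leaves the event-free wait before treatment credited to treatment.
5. Use delayed entry at enrolment for every patient enrolled after t0. This covers those enrolled retrospectively during follow-up and, if the index event is chosen, those enrolled prospectively at diagnosis.

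The cost is protocol wording and slightly more analysis work. Recorded healing times will be somewhat longer than on the EMB clock, more so under the index-event option when clinical suspicion long precedes diagnosis. Confounding by indication remains and needs its own handling. No change to clinical management is involved.
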